--	---

	
related confidence intervals. Patients lost to follow-up or starting a new therapy without PD will be censored for time to event analyses at their most recent disease assessment.
 
Pharmacokinetic and Pharmacodynamic analysis
 
Pharmacokinetic evaluation: Results of SPECT/CT imaging to determine infected cells and kinetics of virus spread and elimination will be summarized by dose and time by descriptive statistics and displayed graphically.
 
Pharmacodynamic evaluation: tissue analysis for MV-NIS, tissue analysis for tumor micro environment and assessment of neoantigens and tumor specific immune response will be summarized by dose and time by descriptive statistics and displayed graphically.
 
Exploratory outcome measure/analyses (analysis will be detailed in the SAP)
 
Data will be gathered for a number of laboratory correlative variables for each patient. Descriptive statistics and simple scatter plots will form the basis of presentation of these data. Correlations between these laboratory values and other outcome measures will be carried out by standard parametric and nonparametric correlation procedures (Pearson's and Spearman's coefficients). Prerequisite normality testing of these data will be carried out via standard Shapiro-Wilk testing (Shapiro and Wilk 1965).
 
Where patterns of correlation are indicated, ordinary and partial correlation coefficients (controlling for dose levels) will be calculated. Inferential testing for significant shifts in the correlative laboratory data results across dose levels will be carried out only as a hypothesis- generating exercise. The small cell size will mean, for example, that only a shift of 1.5 standard deviations in the sample means can be detected via a one-sided Wilcoxon procedure with a 5% type I error rate. In all such situations, confidence intervals will be presented as the primary method of analysis. Hence, such hypothesis testing will only be used as exploratory for directing further research.
 
Ancillary timed endpoints/analysis: exploratory analysis may be carried out on time-related variables MV-NIS cohorts including time until any treatment related toxicity, time until treatment related grade 3+ toxicity and time until hematologic nadirs (WBC, ANC, platelets). Simple summary statistics will be supplemented by Kaplan-Meier survival estimates and related confidence intervals (Pepe and Fleming 1991; Lee 1992). The effect of dose and ancillary dichotomized covariates such as age will be explored using log rank testing involving one covariate at a time. Again, the small sample size restricts the generalizability of such testing, but the results will provide preliminary indication for future research in subsequent phase 2 trials.

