## 7. INVESTIGATIONAL PLAN

### 7.1. Overview of Study Design

This is a phase 1, dose escalation study of the combination of intra-tumoral MV-NIS and systemic atezolizumab in patients with recurrent and metastatic NSCLC. After the dose escalation phase of the trial, a dose expansion cohort will further investigate safety, clinical and immune responses at the MTD. [Figure 1](#) shows the study design. The study will involve 9-24 patients in the escalation phase and 15-18 in the expansion cohort, to provide a total cohort of 21 patients for efficacy evaluation at the MTD.

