### 13.1.8. Exploratory outcome measure/analyses (analysis will be detailed in the SAP)

Data will be gathered for a number of laboratory correlative variables for each patient. Descriptive statistics and simple scatter plots will form the basis of presentation of these data. Correlations between these laboratory values and other outcome measures will be carried out by standard parametric and nonparametric correlation procedures (Pearson's and Spearman's coefficients). Prerequisite normality testing of these data will be carried out via standard Shapiro-Wilk testing ([Shapiro and Wilk 1965](#)).

Where patterns of correlation are indicated, ordinary and partial correlation coefficients (controlling for dose levels) will be calculated. Inferential testing for significant shifts in the correlative laboratory data results across dose levels will be carried out only as a hypothesis-generating exercise. The small cell size will mean, for example, that only a shift of 1.5 standard deviations in the sample means can be detected via a one-sided Wilcoxon procedure with a 5% type I error rate. In all such situations, confidence intervals will be presented as the primary method of analysis. Hence, such hypothesis testing will only be used as exploratory for directing further research.

Ancillary timed endpoints/analysis: exploratory analysis may be carried out on time-related variables MV-NIS cohorts including time until any treatment related toxicity, time until treatment related grade 3+ toxicity and time until hematologic nadirs (WBC, ANC, platelets). Simple summary statistics will be supplemented by Kaplan-Meier survival estimates and related confidence intervals ([Pepe and Fleming 1991](#); [Lee 1992](#)). The effect of dose and ancillary dichotomized covariates such as age will be explored using log rank testing involving one covariate at a time. Again, the small sample size restricts the generalizability of such testing, but the results will provide preliminary indication for future research in subsequent phase 2 trials.

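### Dose-adjusted correlations are planned only where a pattern already shows, so an association hidden by dose can be missed and the adjusted values that are reported tend to be too large when the true correlation is modest

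*Combined protocol and SAP*

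**What the plan says.** Section 13.1.8 of the combined protocol and SAP starts from an unspecified set of markers: "Data will be gathered for a number of laboratory correlative variables for each patient". It describes the first look at them: "Descriptive statistics and simple scatter plots will form the basis of presentation of these data". The plots are not said to be drawn by dose.

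It then plans unadjusted correlations without any condition: "Correlations between these laboratory values and other outcome measures will be carried out by standard parametric and nonparametric correlation procedures", naming Pearson and Spearman coefficients. The next step carries a condition: "Where patterns of correlation are indicated, ordinary and partial correlation coefficients (controlling for dose levels) will be calculated". The synopsis (Section 4, statistical methods) opens the same step with "Where patterns of correlation are indicated". Neither place says what counts as a pattern, which coefficient or plot shows it, or who judges it.

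On tests across dose levels the section is cautious: "Inferential testing for significant shifts in the correlative laboratory data results across dose levels will be carried out only as a hypothesis-generating exercise". The heading of 13.1.8 defers detail to the SAP, but Section 13 adds no further rule on correlations.

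**The concern.** By naming a partial correlation, the plan accepts that dose can distort the relation between a marker and an outcome. The dose levels run from 1×10^8 to 1×10^9 (Section 7.1.1, Table 3), and data from several levels may be pooled. Yet the correction is applied only where the uncorrected data already show something.

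This has two consequences. If dose pushes marker and outcome in opposite directions, or simply adds spread to the marker, the pooled data may show no pattern and no adjusted coefficient is calculated. And adjusted coefficients that appear only after a look have been selected partly for size.

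Several exploratory objectives in Section 6.3 relate immune or genomic markers to clinical response, and the results are meant to guide later research. With roughly 27 to 33 patients, missed leads and inflated leads are the main ways such an analysis can mislead.

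**Working it through.** **The plan's own figures.** The plan states no figure for the correlations. The only number in 13.1.8 concerns shifts between dose levels: "only a shift of 1.5 standard deviations in the sample means can be detected via a one-sided Wilcoxon procedure with a 5% type I error". It gives neither power nor cell size, so it cannot be reproduced. A 1.5 SD shift has exact one-sided Wilcoxon power of 44% at 3 vs 3, 75% at 6 vs 6 and 82% at 7 vs 7. That figure does not bear on the condition examined here.

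**Inputs from the documents.** There are three escalating dose levels (Section 7.1.1), 9-24 escalation patients and "15-18 in the expansion cohort, to provide a total cohort of 21 patients for efficacy evaluation at the MTD" (Section 7.1).

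**Assumptions.**
- The MTD is level 3. Patients per level are 3/3/21 (9 escalation + 18 expansion = 27) or 6/6/21 (18 + 15 = 33).
- The within-dose correlation ρ is 0.3 or 0.5, with normal, uncensored variables.
- Marker and outcome shift linearly by b_m and b_o within-dose SDs per level.
- The look is either an ordinary two-sided p<0.05 or an ordinary correlation beyond ±0.2. For n = 33 the first means beyond ±√(2.040²/(31 + 2.040²)) = ±0.344.

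**Step 1: how dose hides an association.** With V the variance of dose level, the pooled correlation is

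r = (ρ + b_m·b_o·V) / √[(1 + b_m²V)(1 + b_o²V)].

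For 6/6/21, V = 219/33 − (81/33)² = 0.612. For 3/3/21, V = 204/27 − (72/27)² = 0.444. At 6/6/21, ρ = 0.5 and b_m = 1:
- b_o = 0: 0.5/√1.612 = 0.39.
- b_o = −0.5: (0.5 − 0.306)/√(1.612 × 1.153) = 0.14.
- b_o = +0.5: (0.5 + 0.306)/√(1.612 × 1.153) = 0.59.

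Complete masking with equal and opposite trends needs b = √(ρ/V): √(0.5/0.612) = 0.90 SD per level, or √(0.5/0.444) = 1.06 at 3/3/21.

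**Step 2: power.** Simulation used rank correlations, with partial r = (r_xy − r_xd·r_yd)/√[(1 − r_xd²)(1 − r_yd²)] tested on n − 3 degrees of freedom at two-sided 5%. Two-step means that the pair passes the look and its adjusted coefficient is significant. Results for 6/6/21, ρ = 0.5, marker +1 SD per level:

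| Outcome per level | Adjust every pair | Two-step, p<0.05 look | Two-step, ±0.2 look |
|---|---|---|---|
| Flat | 78% | 55% | 74% |
| −0.5 SD | 77% | 8% | 32% |
| +0.5 SD | 79% | 79% | no loss |

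The losses are 78 − 55 = 23 or 78 − 74 = 4 points in the first row, and 77 − 8 = 69 or 77 − 32 = 45 points in the second. In the third row the looser look passes every pair that the stricter one passes, so it loses nothing either.

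At 3/3/21 the flat case gives 69% against 51% (p<0.05) or 67% (±0.2). The falling case gives 67% against 17% (p<0.05). With no dose trend, adjusting costs 1-2 points compared with the ordinary coefficient (82% to 81% at 6/6/21, 73% to 71% at 3/3/21).

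**Step 3: size of the reported coefficient.** For a true 0.3 with a flat outcome, the adjusted coefficient averages about 0.27-0.28 over all pairs, 0.44-0.49 among pairs passing a p<0.05 look, and 0.36-0.37 among those passing a ±0.2 look. A separate check with Pearson coefficients shows that this is not universal. With opposite trends of 1 SD per level, a true 0.3 averages only 0.01-0.14 among pairs that pass. With same-direction trends of 1 SD per level, a true 0.5 averages 0.50.

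**The case against.** **The plan sets no significance gate.** It describes plots and descriptive statistics. Under the looser look the loss in the flat case nearly disappears (74% against 78%). This stands, and it is why both looks are shown. It does not rescue the opposing-trend case (32% against 77%).

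**The large losses need dose and within-dose relations of opposite sign.** No document gives any dose-marker trend. When marker and outcome move together with dose, nothing is lost. This also stands.

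**Every reported coefficient is selected.** A reader might infer this. The text does not support it: the sentence before the condition plans unadjusted correlations with no gate. The two sentences leave it unclear whether ordinary coefficients are also restricted, so selection applies clearly only to the adjusted ones.

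**The intervals named as the primary method are invalid.** A reader might infer this too. The sentence that gives confidence intervals that role follows the text on testing shifts across dose levels and is not clearly about correlations.

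**The adjusted coefficient should be the main result.** If dose acts through the marker, adjustment removes real signal. With a true 0.5 and a marker shift of 1 SD per level, ordinary power is 94% against 79% adjusted (6/6/21), or 85% against 70% (3/3/21).

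**Much of the analysis is insulated.** Patients at the MTD share one dose, where ordinary and partial coefficients coincide, and Section 13.1.7 summarizes pharmacodynamic markers by dose. Clinical response is binary, so absolute power would be lower than shown: 41-49% adjusted, for a 20% response rate and no dose trend. These points limit the consequence. They do not give the condition a purpose.

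**Conclusion.** The point holds as a minor one. The condition is stated protocol text, it is undefined, and it is applied to data not said to allow for dose. It guards against spurious patterns but not against concealed ones. The cost ranges from nothing (same-direction trends) through 4-23 points of power (outcome flat) to 45-69 points (opposing trends), for 6/6/21 patients, a within-dose correlation of 0.5 and a marker rising 1 SD per level. All of these rest on assumed trends, correlations and looks.

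Overstatement of the adjusted coefficient is a tendency when the true correlation is modest. A reader might conclude that reported values are always too large, but the calculations do not bear that out: inflation can vanish or reverse under strong dose trends. The MTD, safety and ORR analyses do not depend on these correlations.

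**What to change.** In 13.1.8 and the matching synopsis text, delete the opening condition ("Where patterns of correlation are indicated"). List the marker-outcome pairs in the SAP. For every listed pair, report the ordinary and the dose-adjusted coefficient side by side, each with a confidence interval, whether or not a pattern is visible. This also settles whether ordinary coefficients are restricted. Do not designate the adjusted coefficient as the main result. A marked difference between the two is itself informative about the role of dose.

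The cost is a change of wording, a longer table and one degree of freedom per adjusted coefficient. No additional data are needed.

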#### 7.1.1. Dose escalation

MV-NIS will be administered once intra-tumorally, to a single tumor, with a 21-gauge needle, Quadrafuse®, or other suitable needle using ultrasound or CT guidance on day 1 of treatment in 3 escalating dose cohorts, starting at dose level 1 (Table 3).

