**Table 3: MV-NIS Dose Levels**

Dose Level	Number of viruses
-1	$3 \times 10^7$
1	$1 \times 10^8$
2	$3 \times 10^8$
3	$1 \times 10^9$

Atezolizumab will be given per the US prescribing information ([Tecentriq® USPI 2016](#)) at 1200 mg IV on day 15 and then every 3 weeks thereafter until progression of disease, discontinuation due to toxicity, or withdrawal of consent.

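### Splitting age into two groups, and leaving open whether the dose log-rank test uses dose order, can waste power in optional exploratory toxicity analyses; the repair is one sentence

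*Combined protocol and SAP*

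**What the plan says.** The last paragraph of Section 13.1.8, repeated in the synopsis under exploratory outcome measures, concerns ancillary timed endpoints: "exploratory analysis may be carried out on time-related variables MV-NIS cohorts including time until any treatment related toxicity", time to related grade 3 or worse toxicity, and time to hematologic nadirs. The method is one sentence: "The effect of dose and ancillary dichotomized covariates such as age will be explored using log rank testing involving one covariate at a time". No cut-point, dose score, trend version or reference distribution for the p-value is given.

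The section heading defers detail: "Exploratory outcome measure/analyses (analysis will be detailed in the SAP"). The document as available gives no further detail on these tests. The plan adds its own caveat: "the small sample size restricts the generalizability of such testing, but the results will provide preliminary indication for future research".

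The doses are ordered. Section 7.1.1 plans treatment "in 3 escalating dose cohorts, starting at dose level 1", and Table 3 ("MV-NIS Dose Levels") lists 1×10^8, 3×10^8 and 1×10^9, with a conditional level −1 at 3×10^7. On numbers, Section 7.1 states: "The study will involve 9-24 patients in the escalation phase and 15-18 in the expansion cohort". The aim given there for these numbers is "to provide a total cohort of 21 patients for efficacy evaluation at the MTD".

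**The concern.** Cutting a continuous covariate in two discards information that has already been collected. With no cut-point fixed, it also leaves a choice open until the data are seen. A log-rank test that treats ordered doses as unlabelled groups spreads its power over patterns that nobody expects.

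In addition, 3 or 6 patients at a lower dose set against 21 at the MTD is a layout in which the chi-square approximation to a multi-group log-rank test can be poor. A nominal 5% p-value may then not mean 5%.

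At stake is how much these analyses can say to the later phase 2 trials that the plan expects them to inform.

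**Working it through.** **The plan's own figures.** None exist for these tests: no power, effect size, event count or alpha. The only full design calculation is the response-rate rule in Section 13.1, at least 8 of 21. Exact binomial gives P(X ≥ 8 | 21, 0.20) = 0.04305 and P(X ≥ 8 | 21, 0.45) = 0.80293, matching the stated 0.043 and 80.29%. That rule is sound and does not depend on the sentence at issue.

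**Inputs.** From the documents: three planned levels; 21 patients at the MTD; 9 + 15 = 24 to 24 + 18 = 42 patients in all. If the MTD is level 3 and each lower level has 3 or 6 patients, the layouts are 3/3/21 (27 patients) or 6/6/21 (33 patients). Assumed: proportional hazards, normally distributed age split at the median, a log-linear dose effect, and a two-sided 5% level.

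**Step 1, age, large-sample.** Power of the continuous test is P(χ²₁(λ) > 3.84). A median split of a normal covariate keeps 2/π = 64% of the information, so λ becomes 0.637λ. For 80% power, λ = (1.960 + 0.842)² = 7.85, and 0.637 × 7.85 = 5.00.

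| Power, continuous age | Power, median split | Loss (points) |
|---|---|---|
| 20% | 14.4% | 5.6 |
| 30% | 20.8% | 9.2 |
| 40% | 27.5% | 12.5 |
| 50% | 34.6% | 15.4 |
| 80% | 60.9% | 19.2 |

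**Step 2, age, simulated with frequent events.** Exponential times, exponential censoring with mean 2 (about one third censored under the null), 3,000 trials per cell; the standard error of a power is at most √(0.25/3000) = 0.9 points.
- HR 1.65 per SD, n = 27: 47.2% against 32.4%, a loss of 14.8.
- HR 1.65 per SD, n = 39: 62.6% against 44.0%, a loss of 18.6.
- HR 2.0 per SD, n = 27: 72.0% against 52.2%, a loss of 19.8.

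Over a wider grid (n = 9 to 36, HR 1.5 to 2.5 per SD) the loss ran from 1 to 23 points, smallest at n = 9.

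**Step 3, age, rare events.** The MTD rule allows at most 1 DLT in 6, which is 17%. With about 17% events and n = 27, the loss is about 8 points at HR 1.65 per SD (19% against 12%, before rounding) and 13 to 15 points at HR 2.0.

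**Step 4, dose, large-sample.** A trend test has 1 degree of freedom and an unordered log-rank over three levels has 2. At λ = 7.85, P(χ²₂(λ) > 5.99) = 70.9%, so 80.0% falls by 9.1 points. For trend-test power of 20% or more, the loss is at most 10.5 points and is about 5 at the low end.

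**Step 5, dose, simulated with frequent events** (same model as Step 2, HR 2.0 per level):

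| Layout | Trend | Unordered | Loss (points) | Null rejection, unordered | Null rejection, trend |
|---|---|---|---|---|---|
| 3/3/21 | 45.1% | 33.6% | 11.5 | 10.6% | 7.3% |
| 6/6/21 | 70.7% | 59.0% | 11.7 | 8.2% | 5.7% |

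Repeat runs gave null rejection of 10.0% and 7.9% for the unordered test. With HR 2 to 8 per tenfold dose, the power difference was −3 to 9 points in balanced layouts (3/3/3 and 6/6/6), 3 to 14 in 3/3/21 and 2 to 11 in 6/6/21.

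**Step 6, dose, rare events** (17% at the MTD, HR 2 per level). Trend against unordered: 0.7% against 2.1% (3/3/21) and 2.6% against 1.5% (6/6/21). Neither test can detect anything. Null rejection of the unordered test was 7.8% and 5.0%.

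**The case against.** **The text does not say the test is unordered.** A log-rank trend test is also log-rank testing, and detail is deferred to the SAP. A reader might infer that the plan ignores dose order and that its p-values are wrong. The documents support neither statement: they name no test version and no chi-square reference, so a trend version or a permutation p-value is not excluded. What stands is that the plan does not say.

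**The size of the loss.** A reader might apply one figure of 12 to 20 points to both age and dose. That fits age only when the continuous test has roughly 40% to 90% power, and it is too high for three dose levels. One could also argue for a larger dose loss: with both tests calibrated to a true 5%, power was 38% against 11% (3/3/21) and 69% against 48% (6/6/21). Those gaps show that inflated size flatters the unordered test, but they rest on the frequent-event model. There a patient at the top dose has hazard e^1.4 = 4.06 against a censoring hazard of 0.5, so 4.06/4.56 = 89% have the event. That may suit toxicity of any grade. It sits badly with grade 3 or worse toxicity under an MTD rule of at most 1 in 6, although DLTs are limited to 36 days and exclude events related only to atezolizumab.

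**Importance.** It is tempting to say that this weakens the central dose-finding question. It does not. Sections 7.1.2 and 13.1.4 settle the MTD by 3+3 DLT counts, reported with exact intervals. The timed analyses are optional, exploratory and carry the plan's own caveat.

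**The remedy has limits too.** The asymptotic trend test is mildly inflated in 3/3/21, and a Cox model on about five events is fragile. Both points stand and shape the fix.

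**Conclusion.** The point holds as a cheap improvement. The plan commits to dichotomising covariates such as age and leaves the use of dose order unstated, for optional exploratory endpoints.

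- **Age:** a median split costs about 6 to 20 points of power. With about 17% events and 27 patients it costs about 8 points at HR 1.65 per SD and 13 to 15 at HR 2.0.
- **Dose, if the test is unordered:** about 5 to 12 points with three levels and frequent events, and nothing useful to lose when events are rare.
- **Type I error, if the test is unordered with a chi-square reference:** about 8 to 10% rejection under the null in the 6/6/21 and 3/3/21 layouts with frequent events.

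Every figure is conditional on assumed effect sizes, event rates, proportional hazards and a median cut, because the documents supply none of these. The MTD and response-rate decisions do not change.

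**What to change.** Replace the sentence in Section 13.1.8 and in the synopsis with:

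*The effect of dose will be explored with a log-rank test for trend across ordered dose levels, with a permutation p-value. Age and other continuous covariates will be entered as continuous variables in single-covariate Cox models, reporting the hazard ratio with 95% CI (profile-likelihood or penalised when events are few).*

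Keep Kaplan-Meier curves by dose and by age group for display. If a trend test was always intended, the same sentence settles the ambiguity.

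The cost is one sentence in two places, with no new data and no change to any dose or clinical rule. The drawback is some loss of power if an effect is non-monotone; the grouped curves would still help to show such a pattern.
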